9.5.3 Resource utilization

Data relating to resource utilization will be used for the purpose of economic evaluation which will be carried out and reported as a separate activity.

9.5.4 Pharmacokinetics

PK concentrations below the limit of quantification will be treated as zero in summary statistics and for the calculation of pharmacokinetic parameters by non-compartmental analysis. Descriptive statistics of pharmacokinetic parameters will include arithmetic mean, geometric mean, standard deviation, median, minimum and maximum, etc. Parameters such as AUC_{inf}, AUC_{last}, AUC_{0-t}, C_{max} and T_{max} will be reported using non-compartmental method of analysis (using Phoenix 6.4 or higher).

9.7 Interim safety review

Safety laboratory data and adverse events will be monitored continuously throughout the study using data management's data review reports.

If there is no significant LFT elevations observed in a cohort at Day 15 (see [Table 3-1](#)), the next cohort with escalated KAE609 doses will start after informing the safety review committee about the findings.

If any significant LFT elevation is observed at Day 15 in any patient(s) in a cohort (see [Table 3-1](#)), a comprehensive safety data review will be performed after all the patients in the cohort have been followed up for 28 days post-treatment.

The safety review committee can pause recruitment and trigger safety review any time based on safety signals. An earlier review of the safety data by the safety review committee/Novartis in the middle of a cohort would be initiated based on occurrences of LFT elevations in the cohort as specified below:

- The number of patients meeting the primary safety endpoint in a treatment arm is at least 2 in Cohorts 1 and 2 or at least 3 in Cohorts 3, 4, 5 and 6.

Data management's data review reports will be provided to the safety review committee and the appropriate Novartis relevant internal and external people who will make decision about whether a KAE609 dosage regimen is safe and can be escalated to the higher dosage. Although the randomization data are not included in the data management system, the study drug (KAE609 QD 1 day, KAE609 QD 3 days, Coartem) and dosage taken by each patient is available in the dosage records. No formal interim safety analysis by treatment group will be performed.

In case that more comprehensive safety analyses by treatment group are needed at the end of cohort or in the middle of cohort, formal interim safety analyses of selected safety or efficacy parameters by treatment group will be provided as described in the safety review charter.

9.8 Sample size calculation

The incidence of patients experiencing at least 2 CTC grade increase from baseline in ALT or AST is not consistent among KAE609 patient/human challenge studies:

- 3 out of 8 (37.5%) patients in a Study with KAE609 at 10 mg QD.
- 4 out of 11 (36.4%) in a Study with KAE609 at 75 mg QD.
- 1 out of 25 (4%) in a Study with KAE609 at 10 to 30 mg QD.
- 1 out of 21 (4.8%) in a Study with KAE609 at 30 mg QD X3.

9.8.1 Single arm approach

[Figure 9-1](#) and [9-2](#) present the probability of observing at least 2 and 3 safety events, respectively, in a treatment group by various sample sizes and true event rates to assess the operational characteristics for the proposed sample sizes.

Given the proposed sample sizes in the treatment groups within each cohort, the probability of observing at least 2 safety events in 10 patients or 3 safety events in 20 patients is at least 80% if the true event rate is $\geq 30\%$ and less than 5% if the true event rate is $\leq 3\%$. Specifically:

- For a sample size of 10 patients per treatment group, the probability of observing ≥ 2 safety events is greater than 80% if the true event rate is $\geq 30\%$ and less than 5% if the true event rate is $\leq 3\%$ (Figure 9-1).
- For a sample size of 20 patients per treatment group, the probability of observing ≥ 3 safety events is greater than 90% if the true event rate is $\geq 30\%$ and less than 5% if the true event rate is $\leq 3\%$ (Figure 9-2).

Figure 9-1 Probability of observing at least 2 safety events by sample size and true event rate

[figure not shown]
[figure not shown]

Figure 9-2 Probability of observing at least 3 safety events by sample size and true event rate

9.8.2 Power for comparison of KAE609 with Coartem

The comparison between KAE609 doses/regimen with Coartem will help interpretation of liver enzyme elevations in the individual KAE609 treatment arms. In the Pyramax Phase II/III trials (EMA 2012), the incidence of patients experiencing Grade 2 ALT was 3.4%, which was higher than other comparators including Coartem. The incidence rate of adults and adolescents experiencing at least 2 CTC grade increase from baseline in ALT or AST in Coartem is about 3%. To assess the power for between treatment comparisons, a Coartem incidence rate of 5% is also considered.

Table 9-1 Power for comparison with Coartem based on 2-sided Fisher exact test

KAE609 true incidence rate	Coartem® true incidence rate	n for KAE609	N for Coartem®	Power for 2-sided testing		
				5% level	10% level	20% level
50%	3%	10	10	50%	70%	77%
		10	20	86%	91%	95%
		10	30	91%	95%	97%
		10	40	94%	97%	99%
		10	50	93%	97%	99%
		10	60	94%	98%	99%
50%	3%	20	10	78%	84%	92%
		20	20	94%	97%	99%
		20	30	99%	99%	>99%
		20	40	99%	>99%	>99%
		20	50	>99%	>99%	>99%
		20	60	>99%	>99%	>99%
50%	5%	10	10	43%	63%	72%
		10	20	80%	86%	92%
		10	30	85%	92%	95%
		10	40	90%	94%	97%
		10	50	89%	94%	97%
		10	60	90%	95%	97%
50%	5%	20	10	71%	77%	86%
		20	20	89%	94%	97%
		20	30	96%	98%	99%
		20	40	98%	99%	>99%
		20	50	99%	99%	>99%
		20	60	99%	99%	>99%
40%	3%	10	10	28%	50%	54%
		10	20	70%	78%	87%
		10	30	77%	87%	91%
		10	40	84%	91%	95%
		10	50	82%	90%	95%
		10	60	83%	92%	95%
40%	3%	20	10	49%	61%	80%
		20	20	81%	88%	94%
		20	30	93%	94%	98%
		20	40	96%	97%	99%
		20	50	96%	98%	99%
		20	60	98%	99%	99%
40%	5%	10	10	23%	43%	50%
		10	20	61%	71%	81%
		10	30	69%	80%	86%
		10	40	77%	85%	91%
		10	50	73%	84%	92%
		10	60	76%	87%	91%
40%	5%	20	10	43%	53%	71%

20	20	72%	81%	89%
20	30	86%	90%	95%
20	40	91%	93%	97%
20	50	93%	95%	98%
20	60	94%	96%	98%

Based on PASS 2011

Given the sample size of 10 to 20 per arm within a cohort, the power to detect treatment difference is low even with large treatment differences using a 2-sided statistical significance level of 5%. If the true rate is 50% for KAE609 and 3% for the Coartem, the power to detect between treatment difference is about 80% using a 2-sided test at the 20% significance level for n= 10 per arm or at the 10% significance level for n= 20 for KAE609 and 10 for Coartem.

If there are at least 2 cohorts at the end of study and the patients treated with Coartem are pooled from all cohorts, the power to detect treatment difference is greatly increased. In case that the study proceeds to the end with 4 cohorts for a total of 40 patients treated with Coartem, the power to detect treatment difference using 2-sided test at the 5% significance level is 77% and 91% for n=10 and 20 patients treated with KAE609, respectively, if the true rate is 40% for KAE609 and 5% for the Coartem. In case that the study proceeds to the end with 6 cohorts for a total of 60 patients treated with Coartem, the power to detect treatment difference using 2-sided test at the 5% significance level is 76% and 94% for n=10 and 20 patients treated with KAE609, respectively, if the true rate is 40% for KAE609 and 5% for the Coartem.

10 Ethical considerations

10.1 Regulatory and ethical compliance

This clinical study was designed and shall be implemented, executed and reported in accordance with the ICH Harmonized Tripartite Guidelines for Good Clinical Practice, with applicable local regulations (including European Directive 2001/20/EC, US CFR 21, and Japanese Ministry of Health, Labor, and Welfare), and with the ethical principles laid down in the Declaration of Helsinki.

10.2 Informed consent procedures

Eligible patients may only be included in the study after providing written (witnessed, where required by law or regulation), IRB/IEC-approved informed consent, or, if applicable after such consent has been provided by a legally acceptable representative(s) of the patient. In cases where the patient's representative gives consent, the patient must be informed about the study to the extent possible given his/her understanding. If the patient is capable of doing so, he/she must indicate assent by personally signing and dating the written informed consent document or a separate assent form. Informed consent must be obtained before conducting any study-specific procedures (e.g., all of the procedures described in the protocol). The process of obtaining informed consent must be documented in the patient source documents.

Novartis will provide to investigators in a separate document a proposed informed consent form that complies with the ICH GCP guideline and regulatory requirements and is considered appropriate for this study. Any changes to the proposed consent form suggested by the

investigator must be agreed to by Novartis before submission to the IRB/IEC, and a copy of the approved version must be provided to the Novartis monitor after IRB/IEC approval.

Women of child bearing potential must be informed that taking the study treatment may involve unknown risks to the fetus if pregnancy were to occur during the study and agree that in order to participate in the study they must adhere to the contraception requirement for the duration of the study. If there is any question that the patient will not reliably comply, they must not be entered in the study.

10.3 Responsibilities of the investigator and IRB/IEC

Before initiating a trial, the investigator/institution must obtain approval/favorable opinion from the IRB/IEC for the trial protocol, written informed consent form, consent form updates, subject recruitment procedures (e.g., advertisements) and any other written information to be provided to patients/subjects. Prior to study start, the investigator is required to sign a protocol signature page confirming his/her agreement to conduct the study in accordance with these documents and all of the instructions and procedures found in this protocol and to give access to all relevant data and records to Novartis monitors, auditors, Novartis Quality Assurance representatives, designated agents of Novartis, IRBs/IECs, and regulatory authorities as required. If an inspection of the clinical site is requested by a regulatory authority, the investigator must inform Novartis immediately that this request has been made.

10.4 Publication of study protocol and results

The key design elements of this protocol will be posted in a publicly accessible database such as clinicaltrials.gov. In addition, upon study completion and finalization of the study report the results of this trial will be submitted for publication and posted in a publicly accessible database of clinical trial results.

10.5 Quality Control and Quality Assurance

Novartis maintains a robust Quality Management (QM) system that includes all activities involved in quality assurance and quality control, including the assignment of roles and responsibilities, the reporting of results, and the documentation of actions and escalation of issues identified during the review of quality metrics, incidents, audits and inspections.

Audits of investigator sites, vendors, and Novartis systems are performed by Novartis Pharma Auditing and Compliance Quality Assurance, a group independent from those involved in conducting, monitoring or performing quality control of the clinical trial. The clinical audit process uses a knowledge/risk based approach. Audits are conducted to assess GCP compliance with global and local regulatory requirements, protocols and internal standard operating procedures (SOPs), and are performed according to written Novartis processes.

11 Protocol adherence

This protocol defines the study objectives, the study procedures and the data to be collected on study participants. Additional assessments required to ensure safety of patients should be administered as deemed necessary on a case by case basis. Under no circumstances is an

investigator allowed to collect additional data or conduct any additional procedures for any research related purpose involving any investigational drugs under the protocol.

Investigators ascertain they will apply due diligence to avoid protocol deviations. If an investigator feels a protocol deviation would improve the conduct of the study this must be considered a protocol amendment, and unless such an amendment is agreed upon by Novartis and approved by the IRB/IEC and health authorities, where required, it cannot be implemented.

- Any clinical event of jaundice (or equivalent term)
- ALT or AST $> 3 \times$ ULN accompanied by (general) malaise, fatigue, abdominal pain, nausea, or vomiting, or rash with eosinophilia
- Any adverse event potentially indicative of a liver toxicity, like hepatic failure, fibrosis and cirrhosis and other liver damage-related conditions; non-infectious hepatitis, liver neoplasms

2. Cardiac

- Absolute QTcF > 500 ms (confirmed by repeat ECGs)

14 Appendix 2: Liver event and Laboratory trigger Definitions and Follow-up Requirements

Table 14-1 Liver Event and Laboratory Trigger Definitions

	Definition/ threshold
LIVER LABORATORY TRIGGERS	
 • $3 \times \text{ULN} < \text{ALT} / \text{AST} \leq 5 \times \text{ULN}$ • $1.5 \times \text{ULN} < \text{TBL} \leq 2 \times \text{ULN}$
LIVER EVENTS (Medically significant events to be reported as SAEs)	
 • $\text{ALT or AST} > 5 \times \text{ULN}$ • $\text{ALP} > 2 \times \text{ULN}$ (in the absence of known bone pathology) • $\text{TBL} > 2 \times \text{ULN}$ (in the absence of known Gilbert syndrome) • $\text{ALT or AST} > 3 \times \text{ULN}$ and $\text{INR} > 1.5$ • Potential Hy's Law cases (defined as $\text{ALT or AST} > 3 \times \text{ULN}$ and $\text{TBL} > 2 \times \text{ULN}$ [mainly conjugated fraction] without notable increase in ALP to $> 2 \times \text{ULN}$) • Any clinical event of jaundice (or equivalent term) • $\text{ALT or AST} > 3 \times \text{ULN}$ accompanied by (general) malaise, fatigue, abdominal pain, nausea, or vomiting, or rash with eosinophilia • Any adverse event potentially indicative of a liver toxicity*

*These events cover the following: hepatic failure, fibrosis and cirrhosis, and other liver damage-related conditions; the non-infectious hepatitis; the benign, malignant and unspecified liver neoplasms
TBL: total bilirubin; ULN: upper limit of normal

Table 14-2 Follow Up Requirements for Liver Events and Laboratory Triggers

Criteria	Actions required	Follow-up monitoring
Potential Hy's Law case ^a	
 • Discontinue the study treatment immediately • Repeat LFTs within 24hHospitalize, if clinically appropriate • Establish causality • Complete liver CRF • Report to Novartis as an SAE 	ALT, AST, TBL, Alb, PT/INR, ALP and GGT until resolution ^c (frequency twice a week until resolution, stabilize or return to within baseline values)
ALT or AST		
$> 8 \times \text{ULN}$	
 • Discontinue the study treatment immediately • Repeat LFTs within 24h • Hospitalize if clinically appropriate • Establish causality • Complete liver CRF • Report to Novartis as an SAE 	ALT, AST, TBL, Alb, PT/INR, ALP and GGT until resolution ^c (frequency twice a week until resolution, stabilize or return to within baseline values)
$> 3 \times \text{ULN}$ and $\text{INR} > 1.5$	
 • Discontinue the study treatment immediately • Repeat LFTs within 24h • Hospitalize, if clinically appropriate • Establish causality • Complete liver CRF • Report to Novartis as an SAE 	ALT, AST, TBL, Alb, PT/INR, ALP and GGT until resolution ^c (frequency twice a week until resolution, stabilize or return to within baseline values)

Criteria	Actions required	Follow-up monitoring
> 5 to ≤ 8 × ULN	
 Repeat LFT within 24 hours If elevation persists, continue follow-up monitoring If elevation persists for more than 2 weeks, discontinue the study drug Establish causality Complete liver CRF Report to Novartis as an SAE 	ALT, AST, TBL, Alb, PT/INR, ALP and GGT until resolution ^c (frequency twice a week until resolution, stabilize or return to within baseline values)
> 3 × ULN accompanied by symptoms ^b	
 Discontinue the study treatment immediately Repeat LFT within 24 hours Hospitalize if clinically appropriate Establish causality Complete liver CRF Report to Novartis as an SAE 	ALT, AST, TBL, Alb, PT/INR, ALP and GGT until resolution ^c (frequency twice a week until resolution, stabilize or return to within baseline values)
> 3 to ≤ 5 × ULN (patient is asymptomatic)	
 Repeat LFT within 48 hours If elevation is confirmed, initiate close observation of the patient 	Investigator discretion Monitor LFT within 1 to 4 weeks
ALP (isolated)		
> 2 × ULN (in the absence of known bone pathology)	
 Repeat LFT within 24 hours If elevation persists, establish causality Complete liver CRF Report to Novartis as an SAE 	Investigator discretion Monitor LFT within 1 to 4 weeks or at next visit
TBL (isolated)		
> 2 × ULN (in the absence of known Gilbert syndrome)	
 Repeat LFT within 24 hours If elevation persists, discontinue the study drug immediately Hospitalize if clinically appropriate Establish causality Complete liver CRF Report to Novartis as an SAE 	ALT, AST, TBL, Alb, PT/INR, ALP and GGT until resolution ^c (frequency twice a week until resolution, stabilize or return to within baseline values) Test for hemolysis (e.g., reticulocytes, haptoglobin, unconjugated [indirect] bilirubin)
> 1.5 to ≤ 2 × ULN (patient is asymptomatic)	
 Repeat LFT within the next week If elevation is confirmed, initiate close observation of the patient 	Investigator discretion Monitor LFT within 1 to 4 weeks or at next visit
Preferred terms		
Jaundice	
 Discontinue the study treatment immediately Hospitalize the patient Establish causality Complete liver CRF Report to Novartis as an SAE 	ALT, AST, TBL, Alb, PT/INR, ALP and GGT until resolution ^c (frequency twice a week until resolution, stabilize or return to within baseline values)
Any AE potentially indicative of a liver toxicity* - severe events only SMQ AE	
 Consider study treatment discontinuation Hospitalization if clinically appropriate Establish causality Complete liver CRF Report to Novartis as an SAE 	Investigator discretion

Criteria	Actions required	Follow-up monitoring

*These events cover the following: hepatic failure, fibrosis and cirrhosis, and other liver damage-related conditions; the non-infectious hepatitis; the benign, malignant and unspecified liver neoplasms
 
^aElevated ALT/AST > 3 × ULN and TBL > 2 × ULN but without notable increase in ALP to > 2 × ULN
 
^b(General) malaise, fatigue, abdominal pain, nausea, or vomiting, or rash with eosinophilia
 
^cResolution is defined as an outcome of one of the following: (1) return to baseline values, (2) stable values at three subsequent monitoring visits at least 2 weeks apart, (3) remain at elevated level after a maximum of 6 months, (4) liver transplantation, and (5) death.
 
Alb: albumin; PT: prothrombin time.
		

15 Appendix 3: Specific Renal Alert Criteria and Actions

Table 15-1 Specific Renal Alert Criteria and Actions

Serum Event	
Serum creatinine increase 25 – 49% compared to baseline	Confirm 25% increase after 24-48h Follow up within 2-5 days
Acute Kidney Injury: Serum creatinine increase \geq 50% compared to baseline	Follow up within 24-48h if possible Consider study treatment discontinuation Consider patient hospitalization /specialized treatment
Urine Event	
New dipstick proteinuria \geq 1+ Albumin- or Protein-creatinine ratio increase \geq 2-fold Albumin-creatinine ratio (ACR) \geq 30 mg/g or \geq 3 mg/mmol; Protein-creatinine ratio (PCR) \geq 150 mg/g or $>$ 15 mg/mmol	Confirm value after 24-48h Perform urine microscopy Consider study treatment discontinuation
New dipstick glycosuria \geq 1+ not due to diabetes	Blood glucose (fasting) Perform serum creatinine
New dipstick hematuria \geq 1+ not due to trauma	Urine sediment microscopy Perform serum creatinine
For all renal events:	

Document contributing factors in the CRF: co-medication, other co-morbid conditions, and additional diagnostic procedures performed
 
Monitor patient regularly (frequency at investigator's discretion) until either:
 
Event resolution: sCr within 10% of baseline or protein-creatinine ratio within 50% of baseline, or
 
Event stabilization: sCr level with \pm 10% variability over last 6 months or protein-creatinine ratio stabilization at a new level with \pm 50% variability over last 6 months.
 
sCr: serum creatinine.
	

16 Appendix 4: Medications, herbs and toxins as cause of ALT/AST elevations

Table 16-1 Medications, herbs and toxins as cause of ALT/AST elevations

Medications and drugs	Herbs and alternative medications
Alpha-methyldopa	Chaparral leaf
Amoxicillin-clavulanic acid	Ephedra
Amiodarone	Gentian
Bosentan	Germander
Carbamazepine	Ji Bu Huan
Dantrolene	Senna
Disulfiram	Kava kava
Etretinate	Scutellaria (skullcap)
Fluconazole	Shark cartilage
Glyburide	Vitamin A
Halothane	Illicit drugs
Heparin	Anabolic steroids
HMG-Co A reductase inhibitors	Cocaine
Isoniazid	Ecstasy (MDMA)
Ketoconazole	Phencyclidine (PCP)
Labetalol	Toxins
Nicotinic Acid	Carbon tetrachloride
Nitrofurantoin	Chloroform
NSAIDs	Dimethylformamide
Phenylbutazone	Hydrazine
Phenytoin	Hydrochlorofluorocarbons
Propylthiouracil	2-Nitropropane
Protease inhibitors	Trichloroethylene
Sulfonamides	Toluene
Terbinafine	
Trazadone	
Troglitazone (withdrawn)	
Valproic Acid

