5.4 Treatment blinding

Treatment will not be blinded to patients, investigator staff, and persons performing the clinical assessments since KAE609 is dosed once daily for one day or 3 days while Coartem is dosed twice daily for 3 days. Since the primary and secondary objectives of the trial are mainly based on objective laboratory assessments, this should not bias the safety endpoint and the efficacy assessments. To reduce the selection bias to treatment groups, IRT will be used to randomize patients to treatment groups and randomization data are kept strictly confidential until formal interim safety review or final analysis. At the time of interim safety review or final analysis, the randomization data will be loaded into the statistical programming system for access to programmers, trial statisticians, and pharmacokineticists.

At the time of formal interim safety review, if needed, summaries of results by cohort and treatment arm, if necessary, will be prepared only for Novartis internal/external experts to make decision for progress to the next cohort. These reports will be performed by the study biostatistics team (or deputy Contract Research Organization (CRO)) and pharmacokineticist if necessary (see [Section 9.7](#)).

Since this is open-label study, unblinding is not needed in the case of patient emergencies (see [Section 5.6](#)).

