5.5.4 Instructions for prescribing and taking study treatment

KAE609

KAE609 can be administered irrespective of the timing of food intake.

Study medication will be administered by the study center personnel with approximately 180-240 ml of water. Each subject's mouth must be checked to ensure that the medication was swallowed. In the case that the patient vomits within 30 minutes of intake a replacement dose will be given to the patient and the investigator or designee will notify IRT. If the second dose is vomited the patient has to be given Coartem as rescue medication.

Coartem

Patients will be dosed BID for 3 days (at the following time points: 0, 8, 24, 36, 48, and 60 hours) and must receive a standard meal within 30 min prior to dosing, as per label. In the case that the patient vomits within 1 hour of intake a replacement dose will be given to the patient and the investigator or designee will notify IRT. If the second dose is vomited the patient has to be given non-lumefantrine standard of care.

Conventional 80/480 mg tablets or 20/120 mg tablets are to be taken orally with a glass of water. The dispersible tablet is to be dissolved in 10 mL of water in a small cup, and subsequently administered orally under hospital supervision; thereafter the cup will be rinsed with an additional 10 mL of water and the content is to be swallowed again.

Coartem medication should be followed whenever possible by food/drink (broth, sweetened condensed milk, etc.) as appropriate.

All dosages prescribed and dispensed to the subject during the study must be recorded on the Dosage Administration Record (DAR) CRF.

All kits of study treatment assigned by the IRT will be recorded in the IRT.

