5.5.5 Permitted dose adjustments and interruptions of study treatment

Additional doses can be given in case of vomiting (see [Section 5.5.4](#)). These changes must be recorded on the Dosage Administration Record (DAR) CRF.

Otherwise, investigational or other treatment dose adjustments and/or interruptions are not permitted.

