5.6.2 Discontinuation of study treatment

Patients will be treated under hospital supervision during the treatment period. Discontinuation of study treatment for a patient occurs when study drug is stopped earlier than the protocol planned duration, and discontinuation can be initiated by either the patient or the investigator. For patients assigned to 1-day treatment arm, they will not be considered as treatment discontinuation if those discontinuation events occur after they have completed the treatment as assigned.

The investigator must discontinue study treatment for a given patient if, on balance, he/she believes that continuation would negatively impact the participation of the patient in the trial.

Study treatment must be discontinued under the following circumstances:

- Patient request
- Pregnancy (see [Section 6.5.6](#) and [Section 7.6](#))
- Use of prohibited treatment as per recommendations in [Section 5.5.8](#)
- Any situation in which study participation might result in a safety risk to the patient and/or any adverse events that in the judgment of the investigator, taking into account the patient's overall status, prevent the patient from continuing participation in the study
- Unsatisfactory therapeutic effect (see [Section 6.5.8](#))

- Emergence of the following adverse events: severe nausea/vomiting, severe pruritus, increases in QTcF to >500 ms (based on repeat Electrocardiograms (ECGs), development of ventricular arrhythmia or clinically significant (symptomatic) bradycardia (see [Appendix 3](#))
- Any laboratory abnormalities (e.g., LFT increase) that in the judgment of the investigator, taking into consideration the patient's overall status, prevent the patient from continuing taking the study medication (see [Appendix 2](#))
- Deviation from the planned dose regimen for the study drug

Patients who discontinue study drug for any of the above reasons may be given rescue medication at the discretion of the investigator and will be followed for the whole study duration until Study Day 29.

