7.3 Liver safety monitoring

To ensure patient safety and enhance reliability in determining the hepatotoxic potential of an investigational drug, a standardized process for identification, monitoring and evaluation of liver events has to be followed.

The following two categories of abnormalities / adverse events have to be considered during the course of the study (irrespective of whether classified/reported as (S)AE):

- Liver laboratory triggers, which will require repeated assessments of the abnormal laboratory parameter
- Liver events, which are considered as medically significant events, i.e., SAEs and which consist of marked elevations of LFTs and / or pre-specified adverse events. These events will require close observation, follow-up monitoring and completion of the standard base liver CRF pages.

Any liver event which meets the criteria for a “**medically significant**” event should follow the **standard procedures for SAE reporting** as described in [Section 7.2](#).

Please refer to [Table 14-1](#) in [Appendix 2](#) for complete definitions of liver laboratory triggers and liver events.

Every liver laboratory trigger or liver event as defined in [Table 14-1](#) of [Appendix 2](#) should be followed up by the investigator or a designated medically qualified person at the trial site as summarized below. Detailed information is outlined in [Table 14-2](#) in [Appendix 2](#).

For the liver laboratory trigger:

- Repeating the LFT within 24 hours to confirm elevation.

These LFT repeats can be performed at a local laboratory to monitor the safety of the subject. If a liver event is subsequently reported, any local LFTs previously conducted that are associated with this event should be reported on the liver CRF pages.

Repeat laboratory tests must be entered on the appropriate unscheduled local laboratory CRF page.

- If the elevation is confirmed, close observation of the patient will be initiated, including consideration of treatment discontinuation if deemed appropriate.

For the liver events:

- Repeating the LFT to confirm elevation as appropriate
- Discontinuation of the investigational drug if appropriate
- Hospitalization of the patient if appropriate
- A causality assessment of the liver event via exclusion of alternative causes (e.g., disease, co-medications)
- An investigation of the liver event which needs to be followed until resolution.

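### Table 14-2's discontinuation instruction for ALT/AST >5 to ≤8 × ULN waits more than 2 weeks, but all study dosing ends by 60 hours, so the instruction can never act

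*Protocol*

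**What the plan says.** **The row.** Table 14-1 lists ALT or AST above 5 × ULN among the liver events to be reported as SAEs. For the band >5 to ≤8 × ULN, Table 14-2 asks for a repeat test within 24 hours and further monitoring if the elevation persists. It then says: "If elevation persists for more than 2 weeks, discontinue the study drug". Nothing else in that row concerns stopping.

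**Its neighbours.** The rows for >8 × ULN, >3 × ULN with INR >1.5, >3 × ULN with listed symptoms, and potential Hy's Law cases call for immediate discontinuation. For isolated total bilirubin above 2 × ULN, after a repeat test, the instruction is "If elevation persists, discontinue the study drug immediately".

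**The regimens.** Section 5.4 of the protocol states that "KAE609 is dosed once daily for one day or 3 days while Coartem is dosed twice daily for 3 days". Section 5.5.4 places the Coartem doses at 0, 8, 24, 36, 48 and 60 hours. Section 5.5.5 allows replacement of vomited doses and adds: "Otherwise, investigational or other treatment dose adjustments and/or interruptions are not permitted".

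**Other sections on stopping.** Section 5.6.2 lists the circumstances in which treatment must be discontinued. They include "Any laboratory abnormalities (e.g., LFT increase) that in the judgment of the investigator" rule out further dosing, with a pointer to Appendix 2. Section 7.3 lists among the actions for liver events: "Discontinuation of the investigational drug if appropriate". For the lower laboratory-trigger band, Section 7.3 asks that stopping be considered once the elevation is confirmed.

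**The concern.** The 2-week clause presupposes a course of treatment longer than 2 weeks, and this trial has none. An investigator who sees ALT at 6 × ULN during a 3-day course and turns to Table 14-2 finds a repeat test, monitoring, and a stopping condition that cannot arise while doses remain. Section 5.6.2 leaves the matter to judgement but sends the reader back to the same appendix.

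The 24-hour repeat raises a further question, because a dose can fall due before the result is back. Section 5.5.5 does not allow that dose to be held, and Section 5.6.2 makes departure from the planned regimen itself a ground for discontinuation. No section says what happens to that dose.

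At stake is consistent handling of a reportable liver event in a trial whose primary objective is hepatic safety. Sites following different sections could give different numbers of doses to patients with the same laboratory result.

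**Working it through.** The plan states no figure to reproduce here. The check is a timeline.

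**Inputs**
- Persistence threshold: more than 2 weeks (Table 14-2), so more than 14 × 24 = 336 h.
- Last planned dose, counted from the first: 0 h for single-dose KAE609 and about 48 h for KAE609 once daily for 3 days (Table 5-1); 60 h for Coartem (Section 5.5.4).
- Entry limit: ALT/AST above 1.5 × ULN is excluded (Section 4.2, criterion 6).
- No interruption that could stretch the course (Section 5.5.5). Replacement applies only to doses vomited within 30 minutes (KAE609) or 1 hour (Coartem) of intake.

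**Earliest time the condition can be met, relative to the last dose.** Take the most favourable case for the rule, an elevation present from the first dose. The gap is 336 h minus the time of the last dose.

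| Regimen | Last dose | Gap |
|---|---|---|
| KAE609 single dose | 0 h | 336 − 0 = 336 h = 14.0 days |
| KAE609 daily × 3 | 48 h | 336 − 48 = 288 h = 12.0 days |
| Coartem twice daily × 3 | 60 h | 336 − 60 = 276 h = 11.5 days |

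**Could the elevation pre-date dosing?** For the rule to act by the last dose, a value above 5 × ULN would have to start at least 11.5 days (Coartem), 12 days (KAE609 × 3) or 14 days (single dose) before the first dose. The 1.5 × ULN entry limit rules this out for an eligible patient.

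**Could later Coartem count as study drug?** Section 5.5.3.2 of the protocol describes rescue Coartem as non-study treatment, and Section 2.4.2 of the SAP calls the Study Day 29 course post therapy. On that classification neither extends study dosing.

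**Where stopping could have any effect.** A single-dose patient has no later dose to stop. Planned numbers, from Section 3.1, the ratios in Section 5.2 and the 60 Coartem patients in Section 9.8.2, are:
- KAE609 single dose: 10 + 10 + 20 + 20 + 20 + 20 = 100
- KAE609 for 3 days (Cohorts 2, 3, 4): 10 + 20 + 20 = 50
- Coartem: 6 × 10 = 60

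The total is 100 + 50 + 60 = 210, which matches the planned enrolment. So 50 + 60 = 110 planned patients have a 3-day course. Cohorts 5 and 6 give KAE609 only as a single dose, so the 3-day courses there are Coartem, about 2 × 10 = 20 patients.

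**Doses at issue.** If the elevation is found before the first Day 2 dose, 2 of 3 KAE609 doses or 4 of 6 Coartem doses remain. If it is found before the first Day 3 dose, 1 of 3 or 2 of 6 remain. The documents do not say how often ALT/AST would pass 5 × ULN that early, or how quickly results return, so these are possible doses and not expected ones.

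**Effect on analysis sets.** The per-protocol and PK sets require at least 80% of study medication (protocol Section 9.1; SAP Section 2.2 and Table 5-9). A 3-day KAE609 patient stopped after one or two doses has 1/3 = 33% or 2/3 = 67% and is excluded. Coartem patients need 5 of 6 doses (83%). Membership of these sets could therefore depend on which section a site followed.

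**The case against.** The strongest reply is that discontinuation is provided for elsewhere. Section 5.6.2 makes it mandatory once the investigator judges that a liver-test abnormality prevents further dosing. Section 7.3 lists it for every liver event where appropriate, and Section 11.1 expects any immediate action that a patient's safety requires. Other rows of Table 14-2 stop treatment at once if symptoms, INR or Hy's Law criteria are also present. All of this stands. A reader might infer that a patient in this band cannot be stopped during the course; the documents do not support that. The limitation belongs to one row and not to the protocol. One qualification concerns Section 7.3: its liver-event line names the investigational drug, which the Glossary defines as the drug being tested. Read literally it does not reach Coartem, whereas Section 5.6.2 covers all study treatment.

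A reader might also infer that the row orders the remaining doses to be given. It does not. It asks for monitoring and is silent on dosing. Nor does Section 5.5.5 forbid permanent discontinuation; it bars adjustment and interruption.

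The reach is also narrower than all arms. Single-dose arms have nothing left to stop. Section 3.6 reports that 50 mg once daily for 3 days had already been given and found safe at interim reviews, so under Amendment 3 mainly the Coartem arms of Cohorts 5 and 6 remain.

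What survives is that the row's one stopping instruction cannot operate, and that the section giving investigators discretion refers them to the appendix containing it.

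**Conclusion.** The point holds in limited form. The discontinuation instruction for ALT/AST >5 to ≤8 × ULN is wrong as written for these regimens: its condition is met no sooner than 11.5 days after the last study dose, so it applies to no patient in any arm. It is an inoperative instruction that does not agree with Sections 5.6.2 and 7.3. Practical consequences are confined to 3-day courses.

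It would be tempting to conclude that the primary result is compromised. The documents do not support this. Patients who discontinue are followed to Study Day 29 (Sections 5.6.1 and 5.6.2), the primary variable is any occurrence over 4 weeks (Section 9.4.1), and the analysis uses everyone who took at least one dose (Sections 9.1 and 9.4.2). The sample size does not depend on the row.

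The conclusion assumes dosing on the planned schedule, entry criteria respected, and Coartem given as rescue or on Study Day 29 not counted as study drug. It should be corrected because the event is a reportable liver event in a hepatic-safety trial and the repair is small.

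**What to change.** Reconcile the action cell of the >5 to ≤8 × ULN row in Table 14-2 with the 1- and 3-day regimens (Table 5-1 and Section 5.5.4) and with Sections 5.5.5, 5.6.2 and 7.3. Sites should have one consistent instruction, executable within the actual course, for the remaining doses while the 24-hour repeat is pending and after the elevation is confirmed. It should be clear whether it applies to Coartem as well as KAE609. Whether the row keeps a stopping condition of its own or defers to the other sections is for the sponsor and its hepatology adviser; no threshold or clinical rule is proposed here.

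The cost is one table cell and its cross-references in a protocol amendment, plus a notice to sites. No extra tests, patients or analyses are needed. The SAP history records an update after database lock. If dosing has ended, the change cannot affect care in this trial; the study report could then state how events in this band were handled during 3-day courses.
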